1.1. Overview of Clinical Studies

Two small investigator-initiated trials (IITs) conducted at Emory University have evaluated ¹⁸F-fluciclovine for PET imaging of brain metastases in adults ([Schuster, 2003](#); [Patel, 2018](#)), with results suggesting efficacy. Both studies reported increased ¹⁸F-fluciclovine uptake in brain metastases: one study in 5 subjects with 9 lesions and another in 12 subjects with 17 lesions. In the larger study, all subjects had prior treatment for brain metastases and had a magnetic resonance imaging (MRI) indeterminate for recurrent disease. Using either biopsy or clinical follow-up as the standard of truth (SoT), 15/15 ¹⁸F-fluciclovine positive lesions were determined to be recurrent disease. On the other hand, the remaining 2 lesions were determined to be radiation necrosis, both of which had low ¹⁸F-fluciclovine uptake.

Apart from brain metastases, other studies have also reported the use of ¹⁸F-fluciclovine in other neuro-oncology settings ([Parent, 2018](#); [Karlberg, 2019](#); [Michaud, 2020](#); [Bogsrud, 2019](#)). This includes one IIT in suspected recurrent primary brain tumor (N=27) ([Michaud, 2020](#)), where tumor uptake of ¹⁸F-fluciclovine provided significantly higher image contrast to ¹¹C-methionine. ¹⁸F-fluciclovine, based on a subset of 3 subjects with indeterminate MRI, was suggested to be potentially useful in this setting. A retrospective analysis of 21 subjects with suspected residual or recurrent high grade glioma ([Bogsrud, 2019](#)) reported high ¹⁸F-fluciclovine uptake in histopathologically / clinically confirmed disease, including the detection of small satellite tumors not previously visualized with MRI in 4 subjects. A recent report of 2 cases has also described the successful use of ¹⁸F-fluciclovine PET-MRI-guided biopsy in post-treatment glioblastoma to distinguish areas of tumor recurrence from areas of predominant treatment effect ([Henderson, 2019](#)). Industry sponsored studies include 4 studies conducted by Nihon Medi-Physics Co., Ltd (NMP) in subjects with treatment-naïve glioma: NMK36-BT-P201 (N=5) ([Kondo, 2016](#)), MK36-BT-P202 (N=40) ([Wakabayashi, 2017](#)), NMK36-BT-P301 and NMK36-BT-P302. These studies collectively suggest the potential for ¹⁸F-fluciclovine to delineate extent of treatment-naïve primary brain tumor beyond contrast-enhancing regions on MRI.

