2. STUDY RATIONALE

Brain metastases are the most common intracranial tumor in adults, occurring in up to 40% of patients with cancer (Suh, 2010; Sinha, 2017), with approximately 200,000 patients affected each year in the USA (Arvold, 2016). Following localized treatment of brain metastases (increasingly, stereotactic radiosurgery [SRS] alongside neurosurgical resection [Kann, 2017; NCCN, 2019]), close follow-up with serial MRI of the brain is performed to evaluate for recurrent disease. Conventional MRI is currently recommended as the main imaging test (NCCN, 2019) following localized treatment, as it is widely available and offers high spatial resolution, with presence of recurrent disease suggested by increased contrast enhancement (CE) depicting anatomical/structural information. However, conventional MRI (CE-T₁ and fluid-attenuated inversion recovery [FLAIR]/T₂-weighted sequences) has limited specificity due to the incidence of treatment-related changes, primarily radiation necrosis (Galldiks, 2019). These treatment-related changes have similar appearances to true recurrence of disease on conventional MRI, including CE, origin near the primary tumor site, vasogenic edema, growth over time, and mass effect (Langen, 2017; Langen, 2018; Pope, 2018).

No specific feature or combination of features on conventional MRI has been established to differentiate between disease recurrence and treatment-related changes, including radiation necrosis and pseudoprogression (Verma, 2013). Specificity of conventional MRI to diagnose recurrent tumor after SRS using visual reads has been reported to be as low as 19% (Peng, 2018), with attempts at validating permutations of neuroradiologist-defined measurements reporting specificities of 32% to 41% (Dequesada, 2008; Stockham, 2012). Alongside the estimated 25% incidence rate of radiation necrosis (Vellayappan, 2018), rates of true local recurrence of disease are similar, ranging from 27% to 31% (Kocher, 2011; Brown, 2010). Therefore, the true prevalence of recurrent disease post-radiotherapy where conventional MRI indicates the possibility of recurrence, can be estimated to be approximately 50%.

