15.1. Estimation of Sample Size

Approximately 150 subjects will be enrolled, to obtain 130 evaluable subjects.

A one-sample binomial exact test will be used to test the following hypotheses in NPA and PPA of ¹⁸F-fluciclovine PET:

NPA

- $H_0(\text{NPA})$: NPA of PET $\leq \text{NPA}_0$
- $H_1(\text{NPA})$: NPA of PET $> \text{NPA}_0$

PPA

- $H_0(\text{PPA})$: PPA of PET $\leq \text{PPA}_0$
- $H_1(\text{PPA})$: PPA of PET $> \text{PPA}_0$

Where NPA_0 and PPA_0 are performance goals for NPA and PPA, respectively.

Performance goals of 50% (NPA_0) for NPA and 50% (PPA_0) for PPA were selected as acceptable thresholds given the setting where SoC imaging is already equivocal. The lower limits for the exact 95% confidence intervals (CI) (Clopper-Pearson method) for both NPA and PPA should be greater than 50%. Assuming an NPA of at least 70% and a PPA of at least 70% for ¹⁸F-fluciclovine PET would need to be observed, a sample size of 130 would achieve 90% power at a 1-sided significance level of 0.025 to reject the performance goals for both NPA and PPA; assuming a brain metastasis prevalence rate of 0.5.

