7.3.3 Demographic and Other Baseline Characteristics

Demographic variables including age, sex, ethnicity and race will be summarized for the FAS and SAF. Age will be as recorded on the eCRF and will not be re-calculated.

Age will be summarized using descriptive statistics, and age group (<65 years old, \geq 65 years old). Sex, ethnicity, and race will be summarized with the number and percentage of subjects in each parameter category.

Baseline characteristics include height, weight, body mass index (BMI), Eastern cooperative oncology group (ECOG) performance status, medical history, and prior treatment history. BMI will be calculated as: weight (kg) / [height (cm) / 100]². Height, weight, BMI and ECOG will be summarized for the FAS and SAF; prior treatment history and medical history will be summarized for the FAS only. Height, weight, and BMI at baseline will be summarized using descriptive statistics. ECOG performance status will be summarized with the number and percentage of subjects with each score (0 to 4).

The number of subjects with confirmed equivocal reference lesions by central neuroradiologist will be summarized.

The prevalence data (% positive reference lesions according to SoR) will be summarized.

Primary tumor origin and the corresponding details such as disease staging and molecular profiles, where applicable, will be summarized, along with the extra-cranial (systemic) disease status and time since first known date of diagnosis of brain metastasis(es).

Primary tumor origin will be categorized as Lung Cancer (non-small cell lung cancer [NSCLC] + small cell lung cancer [SCLC]), NSCLC, SCLC, Breast Cancer, Melanoma, and Other (colorectal, pancreatic, kidney, testes, cervix, ovary, head & neck, sarcoma, other). Time (months) since first known date of diagnosis will be calculated as (screening date – first known date of diagnosis of brain metastasis(es))/30.4375. If the date of diagnosis is a partial date and day is not available, then day will be imputed as the 1st of

the month for the purpose of the calculation. If day and month are both not available then the 1st January will be imputed.

Prior cancer treatments for primary tumor will be summarized with the number and percentage of subjects in each of the following categories:

- Surgery
- Lymph nodes dissection
- Radiotherapy
- Other ablative techniques
- Drug therapy

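### The stated 90% power for both NPA and PPA holds only for each goal taken singly, in one reader, at an exact 65/65 split; for both goals together it is about 79%, and the protocol's own prevalence inputs lower the NPA figure slightly further.

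*Protocol*

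**What the plan says.** Protocol 15.1 sets out the design: "A one-sample binomial exact test will be used to test the following hypotheses", with "Performance goals of 50% (NPA_0) for NPA and 50% (PPA_0) for PPA". The alternative is "Assuming an NPA of at least 70% and a PPA of at least 70" percent. The claim is that "a sample size of 130 would achieve 90% power at a 1-sided significance level of 0.025", and the sentence attaches this power to rejecting both goals, "assuming a brain metastasis prevalence rate of 0.5". The synopsis (Rationale for Number of Subjects) and SAP 7.6 repeat it.

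The prevalence is derived in Protocol section 2 and in the synopsis rationale. Set against a 25% incidence of radiation necrosis, "rates of true local recurrence of disease are similar, ranging from 27% to 31" percent; the protocol concludes that prevalence is roughly 50%.

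Under Protocol 15.5 and SAP 7.4.3, the study succeeds only if the same two of three readers meet both goals. Neither document gives power at another prevalence or sets a minimum number of subjects in either standard-of-reference (SoR) class. The observed figure is only described: "The prevalence data (% positive reference lesions according to SoR) will be summarized" (SAP 7.3.3).

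**The concern.** NPA is tested only in SoR-negative subjects and PPA only in SoR-positive subjects. Power therefore depends on how the 130 divide, and that number is not under the sponsor's control. The plan treats the split as fixed at its expected value. It also attaches to two required goals a figure that the stated test gives for one.

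The prevalence is rounded in one direction: both ends of the range implied by the protocol's rates lie above 0.5, which means fewer SoR-negative subjects than planned. NPA is the specificity measure, and poor MRI specificity is the protocol's main reason for the trial. A reader of the sample-size section would think the chance of missing a goal when both true rates are 70% is 10%. For one reader it is about twice that.

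**Working it through.** **Inputs.** Null rate 0.50 and alternative 0.70 for each goal, one-sided 0.025, 130 evaluable, prevalence 0.5 (Protocol 15.1, SAP 7.6). Necrosis 25%, recurrence 27% to 31% (Protocol section 2).

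**Rule.** For class size n, the critical count r is the smallest value with P(X ≥ r | n, 0.5) ≤ 0.025. This is the same as a Clopper-Pearson lower limit above 50%. Power is P(X ≥ r | n, 0.7).

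**Step 1: reproduce the plan's figure.** 130 × 0.5 = 65 per class. For n = 65, r = 41, attained level 0.0232, power 0.910. The 90% is confirmed for one goal in one reader.

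**Step 2: margin around 65.** Exact power is not monotone in n:

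| n | r | power |
|---|---|---|
| 58 | 37 | 0.879 |
| 62 | 40 | 0.860 |
| 63 | 40 | 0.895 |
| 64 | 41 | 0.878 |
| 65 | 41 | 0.910 |
| 66 | 42 | 0.895 |
| 67 | 42 | 0.923 |

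No n below 65 reaches 0.90. With 130 subjects, both classes therefore reach it only at 65/65. If the true prevalence is 0.50, the chance of 65 or more SoR-negatives is 0.53.

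**Step 3: both goals at a fixed 65/65 split.** For one reader the two goals use disjoint subjects, so given the split their probabilities multiply: 0.910 × 0.910 = 0.828.

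**Step 4: prevalence implied by the protocol's rates.** 27/(27 + 25) = 27/52 = 51.9%. 31/(31 + 25) = 31/56 = 55.4%.

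**Step 5: average over the random split.** Let K ~ Binomial(130, prevalence) be the number of SoR-positives. PPA power is the mean of power(K), NPA power the mean of power(130 − K), and power for both the mean of their product.

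| Prevalence | PPA | NPA | Both |
|---|---|---|---|
| 0.50 | 0.890 | 0.890 | 0.792 |
| 0.519 | 0.902 | 0.877 | 0.790 |
| 0.55 | 0.919 | 0.852 | 0.782 |
| 0.554 | 0.920 | 0.849 | 0.781 |
| 0.64 (assumption, no source in the documents) | 0.953 | 0.758 | 0.721 |

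**Step 6: where the loss arises.**
- Requiring both goals: 0.910 − 0.828 = 0.082.
- Letting the split vary at prevalence 0.50: 0.910 − 0.890 = 0.020 per goal, and 0.828 − 0.792 = 0.036 for both.
- Moving from 0.50 to 0.519–0.554: 0.890 − 0.877 = 0.013 to 0.890 − 0.849 = 0.041 for NPA, and 0.792 − 0.790 = 0.002 to 0.792 − 0.781 = 0.011 for both.

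**The case against.** **The printed figure is not a miscalculation.** It reproduces per goal at 65/65, the prevalence condition is stated openly, and 52% to 55% fits a description of about 50%. This stands. The sentence can even be read as 90% for each goal separately. But it names both goals, and success requires both, so the reader needs the joint figure.

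**The prevalence effect is small.** This also stands. Within the protocol's range PPA gains nearly what NPA loses, and the joint figure moves by about one point. The NPA loss is of the same order as the exact test's sawtooth (58 negatives give 0.879, 62 give 0.860).

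**True performance or the sample may be better than planned.** The alternative is at least 70%, and Protocol section 2 reports specificities of 84% to 93% for related tracers. At a true NPA of 75% and prevalence 0.554, averaged NPA power is 0.97. If all 150 enrolled were evaluable, NPA power at 0.554 and a true rate of 70% would be 0.90, and power for both goals 0.86. These are fair reasons not to fear for the trial, but the printed claim is for 130 subjects at 70%.

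**The success rule covers three readers, not one.** If readers were independent given the truth, each with joint power p = 0.828, the chance that at least two succeed would be 3p² − 2p³ = 0.92 at a fixed 65/65 split. If all three read identically it would stay at 0.83. Readers of the same scans are unlikely to be independent, and the plan states no assumption on this, so the rule cannot be taken as the basis of the 90%. It does mean that the one-reader figures are not the trial's success probability.

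**A stronger reading the documents do not support.** A reader might infer from Protocol 1.1, where 15 of 17 lesions were recurrent and "the remaining 2 lesions were determined to be radiation necrosis", that prevalence is near 88% and the NPA goal badly underpowered. Those are lesions in 12 subjects, whereas the endpoint uses one reference lesion per subject. The protocol itself calls the dataset too small for robust characterization of diagnostic performance. It is also not the only evidence cited for suspected recurrence, since section 2 cites studies of other amino acid tracers. It is not a subject-level prevalence estimate.

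**Conclusion.** The 90% claim is too favourable as worded. At the plan's own inputs it is a single-goal, single-reader figure, valid for each goal only at an exact 65/65 split. For both goals in one reader, power is 0.83 at that fixed split and 0.79 averaged over the split. At the 52% to 55% implied by the protocol's rates, NPA power is 0.88 to 0.85 and power for both goals 0.79 to 0.78. About eight points of the gap come from requiring both goals; the prevalence input alone costs about 1 to 4 points of NPA power and at most about 1 point of joint power.

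This rests on true rates of exactly 70%, 130 subjects with a positive or negative SoR, a binomial split, and one reader. It does not show that the trial is likely to fail, or that true prevalence exceeds 0.5.

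**What to change.** In Protocol 15.1, the synopsis and SAP 7.6, replace the single 90% statement with separate figures for NPA, PPA and both goals, labelled as one reader, at prevalence 0.50 and 0.55. From the table above these are 0.89, 0.89 and 0.79 at 0.50, and 0.85, 0.92 and 0.78 at 0.55. A higher value such as 0.64 (0.76, 0.95 and 0.72) may be added, labelled as an assumption. Say whether the figures are averaged over the split or fixed at the expected count, and state that 90% for a goal needs about 65 subjects in that SoR class.

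Do not take a prevalence from the 15 of 17 lesions. Do not add a rule that declares a missed goal inconclusive below some class size. Any cut-off would be arbitrary because exact power is not monotone, the exact confidence interval in SAP 7.4.3 already shows the imprecision, and a missed goal in a larger class would not prove performance at or below 50% either.

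The success rule, sample size and procedures stay as they are. The cost is some rewording and a less favourable stated power.

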15.2. Analysis Sets

The Full Analysis Set (FAS) will include all enrolled subjects dosed with IMP with an evaluable Visit 2 on-study PET scan. The FAS will be used for primary and secondary non-safety endpoints (including diagnostic performance and inter-reader and intra-reader assessment for the PET scans).

The Safety Analysis Set (SAF) will include all subjects dosed with IMP (with or without the associated PET scan). The SAF will be used for all safety analyses.

15.3. Subject Disposition

Subject disposition will be summarized for all subjects who entered the study. Summaries will include the number and percentage of subjects in each analysis set, completing the study, and discontinuing the study early by the primary reason for discontinuation.

15.4. Demographic and Baseline Characteristics

Demographic variables (including age, sex, ethnicity and race) and baseline characteristics (e.g., height, weight, body mass index [to be calculated], ECOG performance status, medical

history, prior treatment history) will be summarized using appropriate summary statistics for the FAS and SAF.

15.5. Analysis of Primary Endpoint

The primary endpoint for the study is subject-level NPA and PPA (equivalent to specificity and sensitivity, respectively) of ¹⁸F-fluciclovine PET in detecting recurrent brain metastases. Subject-level NPA and PPA will be calculated based on BIE of ¹⁸F-fluciclovine PET compared to SoR on the reference lesion.

Where NPA_0 and PPA_0 are performance goals for NPA and PPA, respectively. Performance goals of 50% (NPA_0) for NPA and 50% (PPA_0) for PPA were selected as acceptable thresholds given the setting where SoC imaging is already equivocal. The analyses for NPA and PPA will be performed using the one-sample binomial exact test. In addition to the rates, exact two-sided 95% CIs according to the Clopper-Pearson method will also be provided. If the pre-defined NPA and PPA goals are met by the same two of three readers (both tests reach statistical significance for the same two readers), the study will be considered to have successfully demonstrated the effectiveness of ¹⁸F-fluciclovine PET in detecting recurrent brain metastases.

15.6. Analysis of Secondary Endpoint(s)

15.6.1. Subject-Level Positive Predictive Value / Negative Predictive Value

Subject-level PPV and NPV of ¹⁸F-fluciclovine PET for detecting recurrent brain metastases will be calculated based on BIE of ¹⁸F-fluciclovine PET compared to SoR on the reference lesion. The point estimates for PPV and NPV, together with the 95% 2-sided exact CI (Clopper-Pearson method) will be presented.

15.6.2. Lesion-Level Diagnostic Performance

Lesion-level diagnostic performance (lesion level PPA, NPA, PPV and NPV) will be calculated based on BIE of ¹⁸F-fluciclovine PET compared to SoR on all lesions (reference, other equivocal and additional PET lesions).

15.6.3. Subgroup Analysis of Diagnostic Performance Data

Subgroup analyses of subject-level PPA, NPA, PPV, and NPV of ¹⁸F-fluciclovine PET, according to primary tumor type and concurrent immunotherapy, will also be presented.

15.6.4. Clinical Utility

Clinical utility endpoints include the following, and will be analyzed as described:

- Number of days taken by the site to establish presence/absence of metastasis by clinical follow-up will be defined as the time from administration of ¹⁸F-fluciclovine to the date the presence or absence of metastasis is determined at site level. If the presence or absence of metastasis is not ascertained by the time the subject reaches the end of the follow-up or when the subject prematurely withdraws from the study, the subject will be censored on the date he/she withdraws from the study. Kaplan-Meier methodology will be used to handle the

censoring of the data, and to estimate the median time to establish presence/absence of metastasis.

- Proportion of subjects with additional metastases identified on ¹⁸F-fluciclovine PET but not on SoC MRI. The estimate of the percentage and the associated 95% 2-sided exact CI will be presented.
- Proportion of subjects whose prospective diagnostic management plan changes following ¹⁸F-fluciclovine PET, by comparing the diagnostic management plans before and after ¹⁸F-fluciclovine PET. The estimate of the percentage and the associated 95% 2-sided exact CI will be presented.

15.6.5. Inter-Reader / Intra-Reader Agreement

Cohen's kappa statistic will be calculated to assess inter-reader and intra-reader agreement on ¹⁸F-fluciclovine PET scan central reads. The statistic will be presented for each pairwise comparison of the 3 readers for the inter-reader agreements, at the subject-level (i.e., reference lesion only) and also at lesion-level (i.e., all lesions defined by site). Similar statistics will be presented for the initial read vs re-read of a subset of PET scans for each reader.

15.6.6. Safety

Treatment-emergent adverse events (TEAEs) are defined as those AEs with onset after the dose of IMP, or existing events that worsened after the dose of IMP during the study, up to 1 day following IMP administration. Verbatim terms of the AEs will be coded to preferred terms (PTs) and system organ classes using the latest version of Medical Dictionary for Regulatory Activities (MedDRA), for data summary purposes. Severity of AEs will be graded using the NCI-CTCAE v5.0. The frequency of TEAEs will be summarized overall, by system organ classes and PT, and by severity. IMP-related AEs and SAEs will also be summarized.

15.7. Planned Interim Analysis

Not applicable.

16. DATA COLLECTION, RETENTION AND MONITORING

16.1. Data Collection Instruments

The investigator will prepare and maintain adequate and accurate source documents designed to record all observations and other pertinent data for each subject administered the study drug. Particular care should be taken to ensure all data points are recorded in source documentation, especially those which are not part of standard practice.

The investigator will collect relevant pre- and post-treatment MRI brain scans at Screening, on-study PET and MRI scans and SoC imaging during study and upload the images to the central imaging core lab.

Documentation of subject cancer history must include:

- Type of primary tumor that gave rise to the brain metastasis.
- Previous treatments for brain metastases.
- Previous cancer treatments for primary tumor.
- Histopathological confirmation of the primary tumor or a metastatic site within 4 years of Screening.

Study personnel at each site will enter data from source documents corresponding to a subject's visit into the protocol-specific eCRF when the information corresponding to that visit is available.

Subjects will not be identified by name in the study database or on any study documents to be collected by the Sponsor and will be identified by a site number and subject number.

If a correction is required for an eCRF, the time and date stamps track the person entering or updating eCRF data and creates an electronic audit trail.

The investigator is responsible for all information collected on subjects enrolled in this study. All data collected during the course of this study must be reviewed and verified for completeness and accuracy by the investigator.

16.2. Data Management Procedures

The data will be entered into a validated database. The Data Management group will be responsible for data processing, in accordance with procedural documentation. Database lock will occur once quality assurance procedures have been completed.

All procedures for the handling and analysis of data will be conducted using good computing practices meeting FDA guidelines for the handling and analysis of data for clinical trials.

